1 STUDY OBJECTIVES

1.1 Primary Objective

The purpose of this study is to evaluate the safety, feasibility and outcome of administering three different statins at submaximal and maximal dose on eCD and dCD. We hypothesize that a pre-operative statin regimen is protective against eCD (12-25h post-CEA) and dCD (30d), and early (365d) mortality. In addition, maximal doses may be essential in achieving optimal neuroprotection against eCD and dCD, with statins that pass the blood-brain barrier achieving similar effects at lower doses due to enhanced entry into the brain. In order to test this, our primary objectives will be:

- 1) Determine whether patients on a pre-existing sub-maximal dose of one of three most commonly prescribed statins (simvastatin <40mg, atorvastatin <80mg, rosuvastatin <20mg) experience a higher incidence of eCD and dCD than those randomized to 218 doses of pre-operative statin supplementation to the maximal FDA approved dose (simvastatin 40 mg, atorvastatin 80 mg, rosuvastatin 20 mg).
- 2) Determine whether approximately 2-18 doses of maximal statin supplementation is sufficient by comparing whether patients randomized to receiving statin supplementation each individually experience a higher incidence of eCD and dCD than those patients on a pre-existing maximal dose of the three most common statins, and whether statins that pass the blood-brain barrier better correlate with reduced eCD and dCD.
- 3) Determine whether patients on no pre-existing statin regimen exhibit less eCD and dCD when randomized to 2-18 doses of pre-operative maximal dose of atorvastatin (80mg) compared to lower dose of atorvastatin (10mg).
- 4) Determine a dose-response relationship to these 3 statins by determining whether all patients at the time of surgery have less eCD and dCD if they are on: 1) simvastatin 40mg rather than on <40mg; 2) atorvastatin 80mg rather than on <80mg; and 3) rosuvastatin 20mg rather than on <20mg.

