20.2%, $P=0.03$) than those not taking statins (2). Within the asymptomatic population, patients taking simvastatin exhibited significantly less eCD than those taking atorvastatin (3.0% vs. 16.0%, $P=0.005$) (Figure 5). There were no other significant pairwise differences in eCD among the other statin types (13). There were significant pairwise differences in HDL among statin types. HDL levels were higher in patients taking simvastatin compared to those taking atorvastatin ($P<0.001$). There were significant pairwise differences in LDL levels only between simvastatin and atorvastatin ($P=0.003$). However, there were no significant differences in triglycerides or total cholesterol levels among the statin types (13). Patients taking statins had significantly lower pre-operative monocyte counts than those not taking statins (7.0 ± 2.0 vs. $8.2\pm 2.1 \times 10^9/L$, $P<0.001$) at the time of surgery. However, there were no differences in monocyte counts amongst the statin types. The central question that we hope to answer is whether statin neuroprotection depends on the type of statin (simvastatin, atorvastatin or rosuvastatin and/or lipophilic versus non-lipophilic) or dose of statin.

A similar decrease in eCD was also seen in symptomatic and asymptomatic patients not taking and taking statins, and if looked at when both groups are analyzed together (symptomatic and asymptomatic patients together): $P=0.04$ (Asymptomatic), $P=0.19$ (Symptomatic), and $P=0.015$ (together).

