2.2.1 Hypothesis

While there are several non-modifiable risk factors for eCD after CEA identified from previous research, including medically treated diabetes mellitus and the presence of the ApoE-ε4 genotype, we have only been able to identify one potentially neuroprotective factor, namely preoperative statin use. Consequently, we hypothesize that in CEA patients:

- 1) A pre-operative statin regimen is protective against eCD (12-25h) and dCD (30d); consequently, early (365d) mortality.
- 2) Maximal doses may be essential in achieving optimal neuroprotection against eCD and dCD, with lipophilic statins or those that pass the blood-brain barrier more easily achieve similar effects at lower doses.

3 **STUDY DESIGN**

[figure not shown]
This is a Phase 3, multicenter, observational (ARM 1), randomized and double-blind study (ARM 2 and ARM 3), and placebo-controlled (ARM 2), where 1,000 carotid stenosis outpatient participants will be assigned to a specific daily statin regimen of no fewer than 2 and no greater than 18 doses prior to their CEA.

We will include patients who are either statin naïve, assuming no history of adverse experience with a statin, or on one of three types of statins: simvastatin, atorvastatin, or rosuvastatin. Patients will be enrolled, and based on their preexisting statin regimen, they will be grouped into one of three arms prior to CEA: ARM 1) Patients on a pre-existing maximal daily dose statin regimen will be observed, ARM 2) Patients on a pre-existing statin regimen at sub-maximal doses will be randomized to maintain their current dose plus placebo or current dose plus the necessary milligrams to reach maximal daily dose, and ARM 3) Patients who are on no preexisting statin regimen, statin naïve in the last 30 days, will be randomized to atorvastatin

10mg or atorvastatin 80mg for no fewer than 2 and no greater than 18 daily doses before their CEA (Figure 6).

As per the simvastatin drug insert, patients taking amlodipine (Norvasc) should not exceed 20 mg of simvastatin; therefore, we will only potentially increase any patient who is also on amlodipine to daily doses of 20 mg and not 40 mg. Consequently:

- *If subject is on 40 mg simvastatin without amlodipine – they will be in ARM 1 (observational)
- *If subject is on 40 mg simvastatin + amlodipine – they will be in ARM 1 (observational)

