We anticipate that patients, who are on a sub-maximal statin regimen, will experience more eCD and dCD than patients on a pre-existing maximal statin regimen or randomized to a maximal statin regimen. We anticipate that patients who are randomized to atorvastatin 10mg will experience more eCD and dCD than patients randomized to atorvastatin 80mg. We anticipate that simvastatin will provide more neuroprotection than atorvastatin or rosuvastatin measured by lower incidences of eCD and dCD at comparable statin doses for lipid lowering. Conclusions regarding the arm of statin naïve patients may be somewhat underpowered depending on the number of statin naïve patients we see. Results will be interpreted with according caution. We expect the randomized nature of the trial to randomly distribute patients with regard to age, diabetes, educational level, pIQ, MCI, perioperative delirium and ApoE-e4, but now have accounted for these in the statistical plan and also include long-term outcomes out to a year as well. Post-hoc assessments will also examine whether the primary findings regarding eCD and dCD apply to subgroups of patients but these analyses will be viewed as hypothesis generating only.

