9.2.1 Treatment Assignment Procedures

The randomization design will be stratified by center, previous use of statin and in random blocks of 4 and 6. The randomization process will be supported by the Statistical Analysis Center (SAC) at the Mailman School of Public Health at Columbia University. SAC will provide a central secure web-based randomization data system. All trials supported by the SAC employ central randomization that takes place in real-time. In other words, the patient's treatment assignment is made at the moment of randomization, based on probabilities calculated according to the randomization scheme, and communicated to the recruiting site via a central source (i.e. a secure web site).

- Patients on maximum dose of one of the three statins will be maintained on that dose (ARM 1). This arm will contain 225 participants.

- Those patients on submaximal doses of the 3 study statins will be randomized to their current dose plus placebo or their current dose plus the additional milligrams necessary to bring to raise them to the maximal daily dose of simvastatin (40 mg) or atorvastatin (80 mg) or rosuvastatin (20 mg) depending on which statin they are already on, (ARM 2). There will be 337 participants maintained at their current dose and 338 raised to the maximum dose of their statins.
- If patients are statin naïve, then they will be randomized to either atorvastatin 10 mg or 80 mg daily (ARM 3). ARM 3 will have 50 participants in each arm.

The randomization will be performed automatically by the web-based data system. No one will have access to unblinded treatment information on a regular basis other than the packaging pharmacy. All handling of study medication will take place using blinded bottle codes. It is not expected that serious adverse events will require revelation of treatment assignment, but the study web site will provide for online unblinding in emergencies. Revelation of treatment assignment will be available only to authorized users, who will be required to provide a clinical justification for unblinding. Each case of unblinding will be addressed by study personnel to ensure access to unblinded treatment assignment information is limited, and that such incidents are limited to circumstances where it is necessary for the health of the patient.

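### Statin type is never randomised, yet it is part of a primary objective, the plan leans on randomisation for balance, and the randomised dose-by-statin contrast is not specified

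*Combined protocol and SAP*

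**What the plan says.** - **The question.** Objective 2 in section 1.1 asks, as part of a primary objective, "whether statins that pass the blood-brain barrier better correlate with reduced eCD and dCD". The preliminary-data text closing section 2.1.5 says: "The central question that we hope to answer is whether statin neuroprotection depends on the type of statin" or on its dose.
- **The hypothesis.** Section 1.1 expects maximal doses to matter, "with statins that pass the blood-brain barrier achieving similar effects at lower doses due to enhanced entry into the brain". Section 2.2.1 repeats that lipophilic statins or "those that pass the blood-brain barrier more easily achieve similar effects at lower doses".
- **The expected read-out.** Section 9.1, Interpretation of Results, anticipates that "simvastatin will provide more neuroprotection than atorvastatin or rosuvastatin measured by lower incidences of eCD and dCD", at doses comparable for lipid lowering. No table of comparable doses is given.
- **The assignment.** Section 9.2.1 raises Arm 2 patients to the maximal dose "depending on which statin they are already on". Arm 1 is observed (section 3) and Arm 3 receives only atorvastatin (section 5.1). "The randomization design will be stratified by center, previous use of statin and in random blocks of 4 and 6"; statin type is not named as a stratum.
- **The balance statement.** Section 9.1: "We expect the randomized nature of the trial to randomly distribute patients with regard to age, diabetes, educational level", and likewise pIQ, MCI, perioperative delirium and ApoE-e4. The sentence goes on to say that these factors have been accounted for in the statistical plan.
- **The analysis.** Sections 9.2 and 9.5 use logistic regression on eCD for all aims. Sections 9.1 and 9.5 adjust for risk factors out of balance between groups at p<0.10. Objective 4 compares maximal with lower dose for each statin, among all patients by their dose at surgery.

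**The concern.** Comparing eCD between simvastatin and atorvastatin users asks whether two differently prescribed groups of patients have equal risk. That is the same as asking whether the drug changes protection only if the groups are otherwise comparable. Randomisation secures comparability for dose within Arms 2 and 3, but not for statin type. A reader of section 9.1 could nonetheless take a between-statin difference as carrying the authority of a randomised phase III trial.

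The stated hypothesis is also not mainly about incidence. If a statin that enters the brain easily reaches a similar effect at a lower dose, raising its dose should gain less than raising the dose of another statin. That is effect modification of dose by statin type. Arm 2 randomises dose within each statin and so can estimate it, but the plan never specifies it.

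**Working it through.** **1. What is randomised, set against what is claimed**

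| Contrast | Basis | Balance from randomisation? |
|---|---|---|
| Added dose v placebo, Arm 2 | randomised | yes |
| 80 mg v 10 mg atorvastatin, Arm 3 | randomised | yes |
| Objective 4, dose within each statin | all patients by dose at surgery, so Arm 1 is pooled with randomised patients | only in part |
| Simvastatin v atorvastatin v rosuvastatin | prescriber's choice | no |

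The balance statement in section 9.1 fits the first two rows. It is made without exception, in the same paragraph as the expectation in the last row.

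**2. The plan's own figures**

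- Arm 2, pooled over statins (section 9.2): 338 v 337 patients, 46.7% detectable reduction, 80% power. The planning eCD rate is not stated. With a two-sided test at 0.05, 80% power corresponds to a control rate of about 14.5%. At the roughly 15% given in section 2.2 for asymptomatic CEA, power is 81.5%. The figure is plausible. No power is given for statin type.
- Preliminary simvastatin v atorvastatin, 3.0% v 16.0%: this corresponds to 2/66 v 15/94. The likelihood-ratio P is 0.0049, matching the stated 0.005 (Pearson P = 0.009). This contrast is itself observational.

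**3. What the Arm 2 interaction could deliver**

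The Arm 2 statin mix is not given. Assume the earlier cohort's mix (section 2.1.5: 94 atorvastatin, 66 simvastatin, 12 rosuvastatin; total 172):

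- atorvastatin 675 × 94/172 ≈ 369
- simvastatin 675 × 66/172 ≈ 259
- rosuvastatin 675 × 12/172 ≈ 47

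Let d be the difference between the two statins' log odds ratios for dose. Then SE² = Σ 1/[(n/2)·p(1−p)] over the four cells, and power ≈ Φ(|d|/SE − 1.96) + Φ(−|d|/SE − 1.96).

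Worked case: atorvastatin falls by 46.7%, from 16% to 8.5%, and simvastatin is flat at 11%.

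- d = logit(0.0853) − logit(0.16) = −0.714
- SE² = 0.0403 + 0.0695 + 0.1578 = 0.2676, so SE = 0.517
- |d|/SE = 1.38, and power = 28%

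| Assumed eCD, lower dose → maximal dose | Power | Simulated | Atorvastatin + simvastatin patients for 80% |
|---|---|---|---|
| atorvastatin 16→3%, simvastatin 3→3% | 55% | 53% | about 1,130 |
| atorvastatin 16→8.5%, simvastatin 3→3% | 15% | 16% | about 6,190 |
| atorvastatin 16→8.5%, simvastatin 8→8% | 24% | not run | about 3,090 |
| atorvastatin 16→8.5%, simvastatin 11→11% | 28% | 29% | about 2,590 |

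Varying simvastatin's share from 20% to 50% of 628 to 675 patients gives 10% to 61% across these scenarios.

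**4. Per-statin dose contrasts**

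At the same mix, Objective 4's simvastatin contrast has about 675 × 66/172/2 ≈ 130 at lower dose. The maximal-dose group is the rest of the 900 × 66/172 ≈ 345 simvastatin users, 345 − 130 = 215. Power for a 46.7% reduction is about 53% at 15% eCD and 16% at 3%. The second value is rough, since 130 × 0.03 is only about 4 expected events. A non-significant simvastatin dose effect is therefore quite possible even when a real one exists.

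**5. Illustration only: confounding of an unadjusted between-statin test**

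Assume 345 simvastatin v 900 × 94/172 ≈ 492 atorvastatin users, no true statin effect, 9% eCD in patients without the risk factor, and a risk factor held by 30% v 50%. An unadjusted test then rejects in 6%, 12% or 28% of trials for a risk ratio of 1.5, 2 or 3. At 25% v 55% it rejects in 9%, 20% or 54%. If the p<0.10 rule is applied to statin type and the factor is measured, rejection returns to about 5% in all six settings.

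**The case against.** The strongest reply is that the plan is not naive. It uses logistic regression for all aims, adjusts for imbalanced factors, collects age, diabetes, ApoE and pre-morbid IQ, qualifies the simvastatin expectation by comparable lipid-lowering dose, and says that prognostic factors have been accounted for. The simvastatin sentence is an anticipation, not a model specification. Objective 4 already plans per-statin dose contrasts.

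Much of this stands, and it rules out several stronger readings that a reader might infer:

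- **That statin types will be compared raw.** Adjustment is planned. What remains is that the plan does not say whether the groups screened for imbalance include statin types, that the screen is data-driven, and that it cannot reach unmeasured reasons for prescribing.
- **That the trial carries a 6% to 54% false-positive rate.** Those figures describe an unadjusted test under assumed imbalances. No passage shows that age or diabetes differs by statin type. The HDL and LDL differences reported between simvastatin and atorvastatin users were seen in patients already on treatment and may be drug effects.
- **That the interaction would settle the question.** Dose is randomised within each statin, but comparing dose effects across statins still compares differently prescribed patients. Nor does it cover a difference in level: section 2.1 reports less eCD on simvastatin across doses other than atorvastatin 80 mg, and equal dose odds ratios at different eCD levels give no interaction on the logistic scale.
- **That the sponsor intends to read non-significance as similarity.** The documents do not say so. They simply do not exclude it.

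**Conclusion.** The point holds in a limited form. Statin type is prescriber-chosen, the question belongs to a primary objective, and the balance statement in section 9.1 cannot apply to it. The contrast closest to Hypothesis 2, the randomised dose effect compared across statins within Arm 2, is absent. Objective 4 does not fill the gap, because it pools randomised with observational patients and never compares dose effects between statins.

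The size of any confounding cannot be established from the documents. The interaction's power of about 10% to 61% rests on an assumed statin mix, the assumed eCD rates above and a two-sided 0.05 test, so it is a supportive estimate rather than a decisive test. No stated sample-size figure is shown to be wrong, and the randomised dose comparisons in Arms 2 and 3 are unaffected. What changes is how strongly the trial may speak about statin type.

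**What to change.** 1. In section 9.1, Interpretation of Results, limit the balance statement to dose within Arms 2 and 3.
2. In sections 9.1 and 9.5, label between-statin comparisons of eCD and dCD as observational and hypothesis-generating. Adjust them for a prespecified set of collected baseline factors: age, diabetes, ApoE, pIQ/education and centre. Leave out LDL, which in existing statin users is an on-treatment value and may carry part of the drug effect.
3. Add a randomised dose group × statin type interaction to the Arm 2 logistic model. Report per-statin dose effects and their difference with 95% confidence intervals as supportive estimates. State the limited power with its assumptions, and that differences across statins may still reflect prescribing.
4. State that a non-significant per-statin test will not be taken as evidence of similar effect at a lower dose.

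The cost is SAP wording and one model term on data already collected. The downside is an imprecise interaction estimate and a weaker statin-type claim.

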9.2 Sample Size and Randomization

Power Analysis

All of the aims will use logistic regression with presence of eCD as the response variable as the primary statistical analysis. A separate independent analysis for dCD will also be performed. Power calculations used data simulations (1000 simulations for each) with power=0.8, $\alpha=0.05$, and expected rates of eCD

based on existing preliminary data. For the comparison between subjects in arm 1 with a maximal dose (N=225) and those in arm 2 beginning with a sub-maximal dose and increasing to a maximal dose (N=338), the estimated minimum detectable effect size corresponds to a 65% reduction in eCD in the former cohort vs. the latter. For the comparison in between subjects in arm 2 beginning with a sub-maximal dose and increasing to a maximal dose (N=338) and those staying at the sub-maximal dose (N=337), the estimated minimum detectable effect size corresponds to a 46.7% reduction in eCD in the former cohort vs. the latter. For the comparison between subjects in arm 3 with 80 mg of atorvastatin (N=50) and those with 10 mg of atorvastatin (N=338), the estimated minimum detectable effect size corresponds to a 91.3% reduction in eCD in the former cohort vs. the latter.

Rationale for Sample Sizes

As per the power analysis above, the 1000 targeted patient enrollment is reasonable considering the aims of this study. We anticipate approximately 350 patients will be scheduled for CEA per year from the six participating institutions (Columbia-Presbyterian, St. Luke's Roosevelt, Cornell University, Valley Hospital, Montefiore Medical Center, and Buffalo Medical Center). Approximately 80% are anticipated to be asymptomatic, leaving 280 per year.

Expecting an approximate 75% recruitment rate, 210 eligible asymptomatic patients will be enrolled each year from the six sites. Over five years, this rate allows for 1000±50 patients to be enrolled. Based on our previous R01 grant, we estimate that a) 225 patients will already be on a pre-existing maximal statin regimen of simvastatin, atorvastatin, or rosuvastatin, b) 675 patients will be on a sub-maximal statin regimen of simvastatin, atorvastatin, or rosuvastatin, and c) 100 patients will be on no pre-existing statin regimen.

For the comparison between subjects in arm 1 with a maximal dose (N=225) and those in arm 2 beginning with a sub-maximal dose and increasing to a maximal dose (N=338), the estimated minimum detectable effect size corresponds to a 65% reduction in eCD in the former cohort vs. the latter. For the comparison in between subjects in arm 2 beginning with a sub-maximal dose and increasing to a maximal dose (N=338) and those staying at the submaximal dose (N=337), the estimated minimum detectable effect size corresponds to a 46.7% reduction in eCD in the former cohort vs. the latter. For the comparison between subjects in arm 3 with 80 mg of atorvastatin (N=50) and those with 10 mg of atorvastatin (N=338), the estimated minimum detectable effect size corresponds to a 91.3% reduction in eCD in the former cohort vs. the latter.

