This aspect of statin neuroprotection has never been explored in detail in humans. Less lipophilic statins than simvastatin may become effective at high concentrations, underscoring the importance of generating a putative dose-response curve. While about 90% of patients at Columbia University Medical Center are already on a statin, we have reason to believe that in more underserved (lower income, less educated) populations, such as those at Montefiore Medical Center in Bronx NY and the University of New York in Buffalo NY, a smaller percentage of patients will be on statins prior to enrollment, and those that are likely to be on diminished doses that preliminary data suggests are less neuroprotective (55). Thus, if we can demonstrate a benefit in the total population, we may also have identified a pre-op therapy that would be particularly important for underserved populations. A second potentially innovative aspect of the proposal concerns the surveillance of systemic inflammation in this population. If certain statin regimes protect against eCD and dCD, whether these regimes are associated with less (or marked changes in) systemic inflammation will be important mechanistic data regardless of the result.

Our previous grant (R01 AG17604) was funded from July 1, 2003 to June 30, 2013. Over the 10 years the grant was funded, and the 15 years we have been studying patients having treatment for CEA, there has been a dramatic change in the incidence of eCD. We have investigated the reason(s) for this change. This analysis has been the primary outcome of this funding period. During our previous R01 grants, we enrolled 878 patients: 620 having CEA, 68 having CAS, and 190 reference patients having either “simple” spine surgery (155 patients) or coronary artery angiography or stenting (34). Of the 620 CEA patients, 559 had full neuropsychometric analysis completed pre- and post-operatively. Of these 559 patients, 231 were symptomatic patients undergoing CEA and 328 were asymptomatic. Symptomatic status refers to whether the patient

has a history of stroke or transient ischemic attack prior to surgery. We significantly surpassed our enrollment goals for all granting periods. All of the neuropsychometric data were analyzed, except for the data from 8 symptomatic and 4 asymptomatic patients because they experienced a peri-operative stroke. We utilized our reference population to account for practice effect and learning due to repeated neuropsychometric testing.

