Additional support for the study rationale comes from the previous study with a cohort of asymptomatic CEA patients and regardless of statin dose or type, where it was found that ~20% of patients' not on statins had cognitive dysfunction compared to 11% of patients on statins.(72) This statistic alone leads us to believe that while a higher dose may be "more neuroprotective," any statin therapy at all will be beneficial to a patient undergoing CEA, and should become standard of care. Although we have evidence to demonstrate the efficacy of statin neuroprotection in CEA, the aim of this study is to reconfirm this and indicate that statin use

should be a standard of care preoperatively. We do not have a dose response curve and are guessing that a high dose is most beneficial. The purpose of this study is to show that. In addition, patients in the first arm of the study who are already on the high dose will be maintained, so no risk there. Patients in the second arm of the study, having already been started on statins, will just maintain the original regimen deemed appropriate by their prescribing physician or a higher, maximal dose, which we hope to demonstrate will reduce the incidence of cognitive dysfunction. Regardless of the randomization, they will be on a dose considered to be suitable for them and we believe they will experience sufficient neuroprotection peri-operatively. As for the third arm of this study, while we would have liked to randomize patients not already on a statin, to placebo or maximal high dose of atorvastatin, we think that providing a low dose may be sufficient. There is no evidence of the most effective dose of atorvastatin or any statin to provide increased benefit. These patients not already on statin therapy, will have ~2 week preoperative statin period which will afford significantly greater protection than going into CEA without any statin therapy. As no patients in this study will be entirely without statin therapy, we feel the benefit of a statin in general (versus no statin) greatly outweighs the issue of optimal (versus sub-optimal) dose.

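### The Arm 3 power statement uses a 10 mg group of 338 where the design has 50, and section 9.2 gives no eCD rate, so the 91.3% detectable reduction cannot be verified for the real design

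*Combined protocol and SAP*

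**What the plan says.** Section 9.2 of the combined protocol and SAP sets the method: "Power calculations used data simulations (1000 simulations for each) with power=0.8, $\alpha=0.05$, and expected rates of eCD" taken from preliminary data. The rates themselves are not given, nor is the sidedness of the test. The model is fixed: "All of the aims will use logistic regression with presence of eCD as the response variable as the primary statistical analysis". No section says whether the model is tested by Wald or likelihood ratio. Section 9.1 adds that dichotomous variables will be analysed with a chi-square test.

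For Arm 3, the Power Analysis paragraph and the repeated paragraph after Rationale for Sample Sizes both compare "subjects in arm 3 with 80 mg of atorvastatin (N=50) and those with 10 mg of atorvastatin (N=338") and conclude that "the estimated minimum detectable effect size corresponds to a 91.3% reduction in eCD in the former cohort vs. the latter". Section 9.2.1 says "ARM 3 will have 50 participants in each arm", and the Rationale expects 100 statin-naïve patients in total.

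For Arm 2 (338 v 337), section 9.2 says "the estimated minimum detectable effect size corresponds to a 46.7% reduction in eCD in the former cohort vs. the latter". Those two groups add up to all 675 patients enrolled in the arm. On the earlier programme, section 2.1.5 reports: "Of the 620 CEA patients, 559 had full neuropsychometric analysis completed pre- and post-operatively".

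**The concern.** The number 338 is the size of the Arm 2 maximal-dose group, quoted one sentence earlier, so it looks carried over. With 338 in the Arm 3 10 mg group, the groups would sum to 225 + 338 + 337 + 50 + 338 = 1,288. With 50 they sum to the planned 1,000.

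The question is whether 91.3% was computed for the real design and printed beside a wrong number, or computed with the wrong number. In the second case the trial would have less power for that effect than stated. Section 9.2 rests its statement that 1,000 patients is reasonable on this paragraph, and readers of a null Arm 3 result will look to it. The Arm 2 line raises a smaller question of the same kind, because it counts every enrolled patient as having an outcome.

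**Working it through.** **Inputs.** Alpha is 0.05 (taken as two-sided), power 0.80, with 1,000 simulations per comparison. The Monte Carlo standard error at 80% power is √(0.8 × 0.2 / 1000) = 1.3 percentage points. Section 9.2 gives no eCD rate, so the control rate p_C is an assumption. I use 15% (section 2.2, asymptomatic CEA), with a range from 12% (section 2.1.5, 2007–2012) to 20.2% (section 2.1.5, asymptomatic patients not on statins). None of these is a rate for statin-naïve patients given 10 mg.

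**Method.** With p_T = p_C × (1 − reduction), power = Σ_a Σ_b Bin(a; n_T, p_T) × Bin(b; n_C, p_C) × 1{test rejects}, summed over every possible 2×2 table. The chi-square test rejects when (a/n_T − b/n_C)² / [p̂(1 − p̂)(1/n_T + 1/n_C)] > 3.84. The likelihood-ratio (LR) test from logistic regression rejects when 2 Σ O ln(O/E) > 3.84.

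**Step 1: reproduce the plan's figures.** One set of rates matches all three percentages: 15% to 8% (1 − 8/15 = 46.7%), 8% to 2.8% (65%) and 15% to 1.3% (91.3%). This set is my reconstruction. Only the figure of about 15% stands in the documents.
- Arm 2, 338 v 337, 15% to 8%: power 82.3% (LR and chi-square). Power reaches 80% for 46.7% at a control rate of 14.3% (LR, chi-square) to 14.5% (Wald). The figure reproduces.
- Arm 1 v Arm 2 maximal, 225 v 338, 8% to 2.8%: 79.1% (LR), 76.3% (chi-square). Consistent under LR.
- Arm 3 as printed, 50 v 338, 15% to 1.3%: 97.3% (LR), 94.4% (chi-square), well above 80%.
- Arm 3 as designed, 50 v 50, 15% to 1.3%: 83.8% (LR), 77.3% (chi-square), on either side of 80%.

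**Step 2: Arm 3 over the range of control rates.** Each cell gives LR / chi-square.

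| Control rate | Power for 91.3%, 50 v 50 | Detectable reduction, 50 v 50 | Detectable reduction, 50 v 338 |
|---|---|---|---|
| 12% | 76% / 66% | 93% / 98% | 83% / 90% |
| 15% | 84% / 77% | 89% / 93% | 77% / 82% |
| 16% | 86% / 81% | 88% / 91% | 76% / 80% |
| 20.2% | 93% / 91% | 82% / 83% | 69% / 72% |

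**Step 3: if 338 really was used.** By chi-square, 91.3% at 50 v 338 has 80% power at a control rate of 11.4%. At that rate the real 50 v 50 design has about 63% (chi-square) to 74% (LR) power.

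**Step 4: sparse events in the 80 mg group.** At a 15% control rate, p_T = 0.15 × 0.087 = 0.01305. Expected events are 50 × 0.01305 = 0.65, and P(no events) = (1 − 0.01305)^50 = 0.52. At 16%, these are 0.70 and 0.50. With no events the estimated log odds ratio is infinite and a Wald test cannot reject. Its power for 91.3% is 21% at 15% and 25% at 16%.

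**Step 5: Arm 2 with missing outcomes.** 559/620 = 90.2%, and 675 × 559/620 = 608.6, about 609 (305 v 304). Power for 46.7% falls from about 82% to about 78% at a 15% control rate, and is 76% to 77% at 14.5%. The detectable reduction is 47.5% to 47.9% at 15% and about 48.5% at 14.5%.

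**The case against.** The strongest reply is that this is a typing error beside a correct figure. At 15%, the rate that also reproduces Arm 2, a 50 v 338 calculation would have given 77% to 82%, not 91.3%. The printed figure lies between the LR and chi-square results for 50 v 50. I accept this as the likelier explanation, but it remains an inference. The Arm 3 control rate need not equal the Arm 2 rate, and at 12% a chi-square calculation with 50 v 338 gives about 90%. Against that, Arm 2's 46.7% has only about 72% power at 12%, so a 12% rate does not fit both.

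A reader might infer that none of the stated detectable effects belong to this trial. The documents do not support that: 46.7% reproduces on the design's own group sizes, and neither defect touches the 65% figure. A reader might also take the pooled 11% in section 2.2 ("had cognitive dysfunction compared to 11% of patients on statins") as the Arm 2 control rate and find power well below 80%. That rate covers every statin and dose, including the high-dose users who would enter Arm 1, so it is a poor guide to sub-maximal users. Section 2.1.5 reports 16.0% for atorvastatin users.

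Two further replies have some force. Section 9.1 concedes that the statin-naïve arm may be underpowered, but ties this to recruitment, not to the group size in the calculation or to sparse events. It also has a missing-data plan, which addresses bias rather than power. Finally, the plan never names a Wald test, so the 21% to 25% figures show why the test should be named. They are not the power of the plan as written.

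**Conclusion.** The Arm 3 group size in the power text is wrong as written, in two places. Because no eCD rate is stated, the 91.3% cannot be confirmed as the detectable reduction of the 50 v 50 design. It cannot be called wrong either: at an assumed 15% control rate it sits inside the 89% to 93% range for that design. The result depends on two unstated inputs, the rate and the test: power for 91.3% runs from 66% (12%, chi-square) to 93% (20.2%, LR).

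The Arm 2 point is secondary. The stated 46.7% holds for 675 patients with outcomes at a control rate of about 14% to 15%. A loss like the earlier programme's 9.8% costs about 4 points of power and moves the detectable reduction by 1 to 2 points. That assumes the earlier completion rate carries over to this trial.

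**What to change.** 1. Change 338 to 50 for the Arm 3 10 mg group in both paragraphs of section 9.2, rerun that simulation, and restate the detectable reduction with its control rate, test and sidedness.
2. Name the Arm 3 test in advance: a likelihood-ratio or Firth-penalised logistic test rather than Wald. The rerun should also report type I error, since large-sample tests need not hold 5% in tables this sparse.
3. State the assumed Arm 2 control rate and restate the detectable reduction on expected evaluable numbers, for example about 609.

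The cost is a rerun of an existing simulation and text edits. The Arm 2 figure becomes slightly less favourable, and the Arm 3 figure may move either way. Enrolment and the 65% Arm 1 comparison stay as they are.
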